6.1 Safety Parameters

Safety end points:

- Fever or pain that develops within 48 hours after the allocated treatment, or any adverse events judged to be related to the treatment.
 - Fever/infection: body temperature $\geq 38.5^{\circ}\text{C}$, leukocytosis (WBC count $>12,000$ /uL) or leukopenia (WBC count $<4,000$ /uL)
 - Pain: new-onset or worsening of pre-existing pain (≥ 1 point increase in VAS).

6.2 Method and Timing

Patients are assessed for vital signs and pain scores every 8 hour after the assigned treatment as per admission routine. Leukocyte count is checked at 48 hours after the assigned treatment, or earlier if fever occurs. Whether the patients develop safety end points are assessed at 48 hours after the treatment and recorded.

6.3 Adverse Event Reporting

Any adverse event (AE) that occurs in randomized patients during the entire trial period should be carefully documented in the electronic case report form (eCRF) regardless of classification, seriousness, intensity, outcome, or causality.

Details of serious adverse events will be communicated by the local investigator to the local institutional review board (IRB).

The investigator should specify and report in the eCRF the nature of the sign or symptom, the date of onset, the date of resolution (duration), the intensity, the causality, interventions performed (if any), the relationship to trial treatment, and the outcome.

In the case of knowledge of an SAE, the investigator must immediately (within one working day of being notified of the event):

- Fill out at a minimum the following items of the internet-based SAE report: date of the AE, term of the AE, patient identification, name of reporter, treatment, result/outcome, assessment of both the seriousness and the relationship to the investigational treatment
- As soon as further information regarding the event is available (e.g. discharge note), the investigator should complete in the documentation in the eCRF and sign it electronically.
- Copies of the discharge note, of all the reports regarding examinations carried out and/or diagnostic findings should be sent to the lead investigator.

Periodic safety reports will be prepared by the lead investigator and forwarded to the IRBs of the participating sites.

6.4 Definitions

Adverse event (AE) is any untoward medical occurrence, unintended disease or injury, or untoward clinical signs including abnormal laboratory findings in patients, whether related to the investigation treatment or not.

- Procedure-related AEs: any event that is judged as causally related to the treatment procedure.
 - ◆ Serious adverse events (SAEs): an adverse event that leads to death, a life-threatening illness or injury, a permanent impairment of a body structure or a body function, in-patient (except the index admission) or prolonged hospitalization, or medical or surgical intervention to prevent life-threatening illness or injury or permanent impairment to a body structure or a body

function.

NOTE:

- Planned hospitalization for a pre-existing condition without serious deterioration in health is not considered an SAE.
- Life-threatening in the definition of an SAE or adverse reaction refers to an event in which the patient is at risk of death at the time of the event. It does not refer to an event which hypothetically might have caused death if it was more severe.

6.5 Adverse Event Follow-up

Follow-up of any SAE that is fatal or life-threatening should be provided within one additional calendar week.

7 Statistical Plan

7.1 Statistical Methods

Descriptive statistics will be computed for all variables and presented. Continuous variables will be summarized by the number of patients, mean and standard deviation. Categorical variables will be summarized by frequency counts and percentages for each category.

The primary efficacy end point will be compared between the two trial groups using a Log-rank test on an intention-to-treat basis. Cox proportional hazards model is used to analyze the rate of POPF closure with adjustment for covariates. Secondary efficacy end points and safety end points are analyzed using Chi-square tests, Fisher's exact tests, two sample T-tests, Mann-Whitney U tests, and multivariable linear and logistic regression models, where appropriate. In all analyses, statistical uncertainty will be quantified by means of 95% confidence intervals.

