1.5 Population

Patients 18 years of age or older who undergo pancreatic resection and subsequently develop POPF (i.e. drain output of any measurable volume of fluid on and after postoperative day 3 with amylase content > 3 times ULN) that persists for longer than 3 weeks are target population of the trial.

During surgery, 7mm-calibered drains are placed before closing the wound; the type, number of drain tubes placed and the location of placement are at the discretion of the operating surgeon. The number and amylase concentration of the drainage fluid is measured on the 3rd, 5th, and 7th postoperative day, and when drainage color changes. POPF is defined as a drain output of any measurable volume of fluid on and after postoperative day 3 with an amylase content > 3 times the upper limit of normal serum level.⁹ After the diagnosis of POPFs, the route of nutrition is (oral, enteral, or parenteral) is at the discretion of the doctor caring the patients. Patients are assessed daily for fistula output and fistula- or treatment-related complications. If fever occurs, broad-spectrum antibiotics are administered and abdominal CT is performed. Additional interventional radiology-guided catheter drainage is performed for any drainable fluid collections identified by CT. If output of a drain tube is below 10 ml during 48 hours, the drain tube is removed. If a drain tube (rarely more than 1) still cannot be removed on day 21 from the onset of POPF, the patient is diagnosed to have a POPF that persists for 3 weeks and further evaluated for eligibility and enrollment.

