3.1 Primary Study Endpoints/Secondary Endpoints

Efficacy end points:

- The primary efficacy end point is the days from the randomly allocated treatment to fistula closure. The date of fistula closure is defined as the date on which the drain is removed after an output of ≤ 10 mL during 48 hours, without recurrence of POPF within the next 3 months.
- Secondary efficacy end points:
 - 30-day fistula closure rate: the proportion of patients in whom the drain can be removed by 30 days after occurrence of POPF, without recurrence of POPF within the next 3 months.
 - Rate of persistent or recurrent POPF after initial drain removal: the proportion of patients with fluid collection^a on follow-up CT, which is to be performed at 3 months after removal of drain or when recurrence of POPF is suspected clinically.
 - Length of hospital stay and hospital costs after the assigned treatment.
 - Rate of fistula-related complications: the proportion of patients who develop fever/infection^b, ileus^c, postpancreatectomy hemorrhage (PPH)^d from undergoing the assigned treatment to end of follow-up.

Safety end points:

- Fever/infection* or pain** that develops within 48 hours after the allocated treatment, or any adverse events judged to be related to the treatment.

[figure not shown]
*Fever/infection: body temperature $\geq 38.5^{\circ}\text{C}$, leukocytosis (WBC count $>12,000$ /uL) or leukopenia (WBC count $<4,000$ /uL)

**Pain: new-onset or worsening of pre-existing pain (≥ 1 point increase in VAS).

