3.6 Duration

If drain(s) cannot be removed after 21 days from the occurrence of POPF, the patient is enrolled and randomized if he or she fulfils the eligibility criteria, and then receives the assigned treatment. After undergoing the assigned treatment, patients are assessed daily for drain output and any complications. Drains are removed when the drainage amount is below 10 ml during 48 hours, and patients are discharged if they tolerate oral intake well and remain afebrile for 2 days after removal of all drains. After discharge, in-office visits were scheduled at week 1, 2, 4, 8, and 12. A follow-up CT is performed when there is clinical suspicion of POPF recurrence, or at 3 months after removal of the drain, whichever comes first. Therefore, the expected duration of subject participation is between 3 to 4 months.

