5.2 Method and Timing

- Days from the assigned treatment to fistula closure: daily fistula output is assessed and recorded after fistulography with or without occlusion. Drains are removed when the drain output is ≤ 10 mL during 48 hours.
- 30-day fistula closure rate: the day on which POPF is diagnosed is day 1. The outcome is assessed at 3 months after initial removal of the drain. If recurrence is noted within 3 months after initial removal of the drain, the fistula is considered not healed by 30 days regardless of whether the drain could be removed by day 30 after the onset of POPF.
- The proportion of patients with persistent or recurrent POPF: a contrast-enhanced abdominal CT (non-enhanced CT is acceptable if contrast injection is contraindicated) is performed 3 months after removal of drains, or when there is suspicion of POPF recurrence, as suggested by the appearance of fever, ileus, or abdominal pain. Any intraabdominal fluid collection larger than 4 cm in its largest dimension is considered as evidence of POPF recurrence.
- Length of hospital stay and hospital costs after the assigned treatment: assessed at the date of discharge.
- The proportion of patients with fistula-related complications (fever/infection, ileus, bleeding/ postpancreatectomy hemorrhage (PPH) that develop after receiving the assigned treatment till 3 months after removal of drains. Patients are assessed daily for these complications during admission, and at week 1, 2, 4, 8, 12 after discharge at scheduled in-office visits.

6 Assessment of Safety

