7.2 Sample Size Estimation

With 2:1 randomization, it is estimated that 51 patients, 34 for the occlusion group and 17 for the standard care group, are needed to have 80% power to detect a hazard ratio for removal of drain of 2.5, on the basis of a log-rank test with a two-sided significance level of 5%. Assuming a 10% dropout rate, the planned number of patients to be enrolled is 57, 38 for the occlusion group and 19 for the standard care group. All randomized subjects are analyzed according to intention-to-treat.

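### The primary log-rank test is valid but leaves pre-randomisation drain output unused; naming it as the single covariate would probably add some power, with a small possible loss

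*Combined protocol and SAP*

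**What the plan says.** - **Primary test.** Section 7.1: "The primary efficacy end point will be compared between the two trial groups using a Log-rank test on an intention-to-treat basis". No stratum or covariate is named. The same section plans a covariate-adjusted Cox model of closure, but lists no covariate and does not make it the primary test.
- **Sample size.** Section 7.2 plans for a hazard ratio of 2.5 with 80% power, "on the basis of a log-rank test with a two-sided significance level of 5" per cent. That gives 51 patients (34 + 17), or 57 (38 + 19) with 10% dropout.
- **End point.** Sections 3.1 and 5.1 date closure as "the date on which the drain is removed after an output of ≤ 10 mL during 48 hours", and add that the fistula must not recur in the following 3 months.
- **Before entry.** Section 1.5: "Patients are assessed daily for fistula output and fistula- or treatment-related complications". It continues: "If output of a drain tube is below 10 ml during 48 hours, the drain tube is removed". Patients become candidates "If a drain tube (rarely more than 1) still cannot be removed on day 21 from the onset of POPF", and section 3.6 agrees: "If drain(s) cannot be removed after 21 days from the occurrence of POPF, the patient is enrolled and randomized".
- **Recording.** Section 5.2 mentions recording only for output after treatment: "daily fistula output is assessed and recorded after fistulography with or without occlusion".
- **Randomisation.** Section 3.3 stratifies by centre only.

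**The concern.** A patient is randomised because drain output has not fallen far enough by day 21, and mostly reaches the end point when it does. The baseline value of that quantity is therefore assessed for every entrant and is an obvious candidate predictor of time to closure. A plain log-rank test leaves whatever it explains in the noise.

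The planned Cox model does not settle this. Its covariates are unnamed, so output may or may not be included, and the choice could be made after outcomes are known.

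What is at stake is efficiency in a 57-patient trial. Neither validity nor the sample size is in question.

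**Working it through.** **1. The plan's own figure.** Schoenfeld events for 2:1 allocation, HR 2.5, two-sided 5%, 80% power:

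d = (1.960 + 0.842)² / [(2/3)(1/3)(ln 2.5)²] = 42.07, rounded up to 43.

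Fifty-one patients supply this if 42.07/51 = 82.5% close; the documents give no closure proportion. Simulating the log-rank test directly with every patient closing (20,000 runs) gives 79.7% power at 32 + 16 and 82.4% at 34 + 17. So 51 is the smallest 2:1 total reaching 80%. With 10% dropout, 51/0.9 = 56.7, hence 57. The stated figures reproduce.

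**2. Model for the check.** Closure hazard = h₀(t)·exp(θ·treatment − β·x), where x is log output before randomisation in SD units.
- From the documents: 38 + 19 patients, blocks of 3, 10% dropout (57 × 0.9 = 51.3 closures), HR 2.5.
- Assumed: β, exponential closure and dropout times, no centre effect.
- Section 7.2 ties 2.5 to the log-rank test, so the crude hazard ratio is held at about 2.5. The conditional one then runs from 2.50 (β = 0) to 2.91 (β = 0.5).
- In terms of correlation between log output and log days to closure, r = β/√(β² + π²/6). This gives 0.23 at β = 0.3 and 0.36 at β = 0.5.

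**3. Power at N = 57.** The first pair compares the planned log-rank (a score test) with a Cox likelihood-ratio test (LRT) adjusted for log output. The second pair comes from separate runs and uses an LRT on both sides. There were 10,000 runs per cell (SE about 0.4 points).

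| Output effect (β) | Log-rank | Adjusted LRT | Unadjusted LRT | Adjusted LRT |
|---|---|---|---|---|
| 0 | 82.5 | 83.3 | 83.5 | 83.0 |
| 0.2, both arms | 83 | 86 | 83.3 | 84.8 |
| 0.3, both arms | 83.5 | 88 | 83.7 | 87.2 |
| 0.5, both arms | 83 | 92 | 84.4 | 92.1 |
| 0.5 control, 0.25 occlusion | 83 | 85 | – | – |
| 0.8 control, 0.4 occlusion | 82 | 86 | – | – |
| 0.5, controls only | 82 | 80 | 82.7 | 80.5 |
| 0.8, controls only | 80 | 76 | 81.6 | 75.9 |

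- Common effect of 0.2 to 0.5: a gain of 3 to 9 points over the planned test, or 1.5 to 7.7 like for like. About 1 point therefore belongs to the choice of test statistic.
- Output irrelevant: 83.5 − 83.0 = 0.5 point lost like for like, and none against the log-rank test.
- Controls only: about 2 to 4 points lost against the log-rank test (1.3 in a repeat run at β = 0.5: 81.9 vs 80.6), and 2.2 to 5.7 like for like.

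**4. Type I error.** With effects of 0 to 0.8 and 20,000 runs per cell: log-rank 5.4–5.6%, adjusted 5.4–5.7%. Smaller repeat runs gave about 5 to 6.5%. The two tests behave alike.

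**5. Robustness at a common 0.5** (log-rank vs adjusted):
- true effect a threshold at the median: 84 vs 90
- linear in raw output: 83 vs 91
- skewed log output: 83 vs 93
- 5% missing, set to the median: 83 vs 91
- whole-day times with Efron ties: 82–84 vs 92

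**6. Centre.** The number of centres is not given. Stratifying the adjusted model by an assumed 3 or 6 centres loses 3–8 points if centres do not differ. It changes power by −2 to +2 points at a between-centre SD of 0.5.

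**The case against.** The strongest case against is that nothing is wrong: test and sample size agree, the test is valid, and the benefit rests on a prognostic strength that appears nowhere in the documents. All of that stands.

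The documents also give reason to expect the unfavourable case. Section 1.1 says occlusion stops flow through the drain, and section 1.2 reports immediate healing in all 20 pilot patients. If so, earlier output may hardly predict closure in two thirds of the trial. If the true effect is also larger than planned, little power is left to gain: at a conditional hazard ratio of 4 (output effect 0.3–0.5), the log-rank test reaches 96–98% and the adjusted test 99%.

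Stronger readings are tempting, but the documents do not support them:
- *The trial is underpowered.* That follows only if 2.5 is a hazard ratio conditional on output. For example, at 51 patients and a closure hazard ratio of 1.5 per SD, the log-rank test would have 74% against 83% adjusted. Section 7.2 ties 2.5 to the log-rank test.
- *Output is the end point, so it must predict closure in both arms.* Closure also needs 3 months without recurrence, and drains are withdrawn 2 cm a day in asymptomatic patients (section 3.5). A shared removal threshold does not show that baseline output is prognostic in both arms. The simulation models neither recurrence nor withdrawal.
- *Adjustment is worth 18 patients.* The log-rank test needs about 75 patients to come close (91.5% vs 92%) only at a common effect of 0.5, the top of the range.

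A lesser remedy is to keep the log-rank test primary and name output in the supporting Cox model. That would close the unnamed-covariate gap but add no power to the primary test.

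**Conclusion.** The point holds as one of efficiency. The primary test is valid and 51/57 is not wrong, but a baseline value the trial already assesses, and which is the main part of the closure definition, is left out of it. The unnamed-covariate Cox model does not make good the omission.

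The size depends on an assumed prognostic strength. Adjustment gains about 2 to 9 points if output acts similarly in both arms (0.2–0.5 per SD), roughly 1 of them from the likelihood-ratio test. It costs at most about half a point if output is irrelevant, and about 1 to 6 points if output acts only in controls (0.5–0.8). With half the effect under occlusion it still gains about 2 to 4. On balance, pre-specified adjustment is worth adopting, with medium confidence. The controls-only case is a real possibility and should be acknowledged.

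**What to change.** Before any outcome data by arm are seen:

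1. Make total drain output over the 48 hours before randomisation a required eCRF item.
2. Replace the primary-analysis sentence in section 7.1 with:

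> The primary p-value, hazard ratio and 95% profile-likelihood confidence interval come from one Cox model (Efron ties) for days from assigned treatment to fistula closure, by intention to treat. Its only covariates are treatment and log 48-hour drain output before randomisation (mL, summed over drains still in place; values below 10 mL set to 10 mL; a missing value takes the median of both arms combined). The p-value is the two-sided 5% likelihood-ratio test for treatment. The unadjusted log-rank test and crude hazard ratio are reported beside it. The same model stratified by centre is a sensitivity analysis.

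3. Add to section 7.2:

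> The figures of 51 and 57 were calculated for the unadjusted log-rank test at a crude hazard ratio of 2.5 and are retained unchanged.

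**Cost.** A protocol amendment (section 7.6), minor programming, and one eCRF field for a quantity already needed for the day-21 drain rule. No extra patients or procedures.

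**Downsides to state openly.** The adjusted hazard ratio is conditional (about 2.9 when the crude one is 2.5, at an output effect of 0.5), so the crude one must appear beside it. A small power loss is possible if output predicts closure only in controls.

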This is a multicenter, investigator initiated, prospective, superiority, parallel-group, randomized, double-blinded trial to compare trans-drain occlusion followed by gradual withdrawal of drain and gradual withdrawal of drain alone.

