3.3 Randomization

Patients fulfilling the inclusion and exclusion criteria will be randomly assigned in a 2:1 ratio to receive embolization or standard care. Block randomization is performed, stratified according to center. For each participating center, a randomization list is produced randomly with block size of 3. The Research Electronic Data Capture (REDCap) software program is used to generate randomization numbers.

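### Randomisation is stratified by centre, but the primary log-rank test does not use centre. The test is valid but conservative, and it loses power if centres differ appreciably in closure speed.

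*Combined protocol and SAP*

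**What the plan says.** The opening of section 3 (Trial Design) describes the trial as follows: "This is a multicenter, investigator initiated, prospective, superiority, parallel-group, randomized, double-blinded trial". Section 3.3 (Randomization) says patients "will be randomly assigned in a 2:1 ratio to receive embolization or standard care", and adds: "Block randomization is performed, stratified according to center". It continues: "For each participating center, a randomization list is produced randomly with block size of 3". No other stratification factor is named, and the number of centres is not given.

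Section 7.1 (Statistical Methods) says of the primary analysis: "The primary efficacy end point will be compared between the two trial groups using a Log-rank test on an intention-to-treat basis". It then adds: "Cox proportional hazards model is used to analyze the rate of POPF closure with adjustment for covariates". For secondary and safety end points it lists chi-square, Fisher, t and Mann-Whitney tests, and "multivariable linear and logistic regression models, where appropriate". It names no covariate for any model.

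Section 7.2 bases the sample size on a log-rank test and does not mention stratification: 51 patients for 80% power at a hazard ratio of 2.5, raised to 57 for 10% dropout.

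**The concern.** Blocking within centre makes the two arms more alike than chance would. An unstratified log-rank test computes its variance as if that had not been done. If centres differ in closure speed, the variance is too large for the design and the test rejects too rarely. Mixing centres with different closure rates also pulls the overall hazard ratio toward 1.

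The protocol gives reason to expect some difference between centres. Section 1.5 says of the drains that "the type, number of drain tubes placed and the location of placement are at the discretion of the operating surgeon", and it leaves the route of nutrition to the treating doctor. Section 4.4 leaves other care to the attending physician. Under section 3.5, continued drain withdrawal depends on the patient being judged asymptomatic, which is a local assessment.

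At stake is power. The trial has 57 patients, a target of exactly 80%, and no allowance for centre differences. In addition, because the covariates are unnamed, the decision on whether to adjust for centre can be put off until the outcomes are known.

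**Working it through.** **The plan's own figure.** Inputs from section 7.2: hazard ratio 2.5, 2:1 allocation, two-sided 5%, 80% power. Schoenfeld's formula gives the number of closures needed:

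D = (1.96 + 0.842)² / [(2/3)(1/3)(ln 2.5)²] = 42.07, so 43.

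The plan's 51 follows if about 84% of patients reach closure (42.07/0.84 = 50.1, rounded up), a proportion the documents do not state. If all 51 close, Schoenfeld power is 87.0%, and simulation gives 83.0%. The dropout step reproduces exactly: 51/0.9 rounds up to 57, and 34/0.9 and 17/0.9 round up to 38 and 19. So 51 is plausible for an unstratified test with identical centres.

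**Assumptions.** The documents give no number of centres, centre sizes, between-centre variation or closure probability. The simulations assume exponential closure times, normal centre effects on the log hazard, permuted blocks of 3 (2:1) within centre, and a cut-off giving roughly 80 to 88% closures at hazard ratio 2.5. To interpret the SD: the median closure-rate ratio between two randomly chosen centres is exp(SD × √2 × 0.6745), which is 1.33 at SD 0.3, 1.61 at 0.5 and 2.14 at 0.8.

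**Type I error** (51 patients, five centres of 21/12/9/6/3, 20,000 trials per setting):

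| SD | Unstratified | Centre-stratified |
|---|---|---|
| 0 | 5.2% | 5.2% |
| 0.3 | 4.8% | 5.3% |
| 0.5 | 4.2% | 5.4% |
| 0.8 | 3.1% | 5.3% |

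With simple allocation that ignores centre, the unstratified test keeps its size (5.2% at SD 0.8). The conservatism therefore comes from pairing stratified allocation with an unstratified test. Power of the unstratified test at SD 0.8 is 57.4% under simple allocation and 57.3% under centre blocking, so this test gains nothing from the blocking.

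**Power with every centre its own stratum** (51 patients, hazard ratio 2.5, unstratified / stratified, %):

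| Centres | SD 0 | SD 0.3 | SD 0.5 | SD 0.8 |
|---|---|---|---|---|
| 3 | 79.5 / 76.8 | 76.3 / 75.8 | 71.1 / 74.6 | 61.2 / 72.4 |
| 5 | 79.5 / 74.3 | 75.0 / 72.7 | 69.3 / 71.5 | 57.3 / 69.3 |
| 8 | 79.5 / 70.6 | 75.0 / 69.3 | 68.9 / 68.3 | 55.3 / 66.2 |

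Full stratification over many small centres is costly: with eight centres it loses 5.7 points at SD 0.3 (75.0 − 69.3).

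**Power with centres under 9 patients pooled** (57 patients, hazard ratio 2.5, about 80 to 85% closures, 4,000 trials per setting, unstratified / pooled-stratified, %):

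| Centres | SD 0 | SD 0.3 | SD 0.5 | SD 0.8 |
|---|---|---|---|---|
| 3 | 82 / 80 | 80 / 80 | 74 / 78 | 64 / 76 |
| 5 | 81 / 77 | 77 / 77 | 72 / 75 | 60 / 73 |
| 6 | 82 / 80 | 79 / 79 | 73 / 76 | 62 / 72 |
| 8 | 81 / 78 | 78 / 76 | 72 / 74 | 59 / 69 |

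The Monte Carlo standard error is about √(0.75 × 0.25/4000) = 0.7 points, so repeat runs differ slightly. Taking the repeats together, for 3 to 8 centres the pooled-stratified test differs from the plan's test by −2 to −5 points at SD 0, 0 to −2 at SD 0.3, +0.5 to +4 at SD 0.5 and +7 to +14 at SD 0.8. A run with five centres of 9 to 15 patients puts the crossover near SD 0.4 (75.7% against 75.8%).

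**The case against.** The strongest reply is that nothing in the documents shows that centres differ much. The steps closest to the end point are common to all sites: 7 mm surgical drains, one output threshold for removal, the same daily withdrawal schedule in both arms, and no somatostatin. The discretion in sections 1.5 and 4.4 belongs to individual clinicians and need not follow centre lines. An SD of 0.8 means a typical closure-rate ratio of about 2.1 between two centres, close to the treatment effect of 2.5. At low variation the stratified test is the weaker one. This stands, and it is why the size of the loss is uncertain.

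Pooling is also an imperfect safeguard. With five centres of 9 to 15 patients nothing is pooled, and the cost at SD 0 is still 4 to 5 points. With seven equal centres (57/7 ≈ 8) a cut-off of 9 would merge them all and bring back the unstratified test. This stands against any threshold chosen without the actual centre sizes.

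A reader might infer that the planned test is invalid. It is not: its type I error falls, so false positives do not become more likely. A reader might also infer that stratifying wins whenever centres differ at all. The gain over the planned test appears only from about SD 0.4 to 0.5. Finally, a reader might conclude that every secondary analysis ignores centre. That is certain only for the simple two-group tests; the regression models neither include nor exclude it.

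None of this removes the mismatch between sections 3.3 and 7.1, or justifies leaving the handling of centre unstated.

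**Conclusion.** The point holds in a limited form. Centre is the only randomisation factor, and the stated primary test does not use it. The consequence is conservatism and lost power if centres differ. Under the assumed patterns of 3 to 8 centres with 57 patients, the unstratified test has about 72 to 74% power at SD 0.5 and 59 to 64% at SD 0.8, against 81 to 82% with identical centres. The pooled-stratified test recovers part of this but does not restore 80%: it reaches 74 to 78% and 69 to 76%.

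The trade is favourable but uneven: a few points lost if centres are alike, against up to 14 gained if they differ strongly. Every figure rests on assumed centre numbers, SDs and closure proportions. Confidence is high for the mismatch and its direction, and low for its size.

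**What to change.** In section 7.1:

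- Make the primary test a log-rank test stratified by centre, and stratify the Cox model by centre. Name any other covariates.
- State a rule for pooling small centres, fixed before outcome data are seen. Fewer than 9 randomised patients is one example; the threshold should be set from the actual centre sizes.
- Keep the unstratified log-rank test as a sensitivity analysis.
- Include centre in the secondary models where numbers allow.

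In section 7.2, recheck the power statement under the stratified test, stating the assumed number of centres and closure proportion.

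The cost is SAP wording and one repeated power calculation, with no added procedures. The statistical downside is about 2 to 5 points of power if centres turn out not to differ. If the sponsor prefers the unstratified test, section 7.1 should say so and explain how centre is handled elsewhere.
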